7.2.3 Translational end-points

1. Assess expression of SSTR1-5 in biopsy specimens and compare with PET parameters
2. Evaluation of possible adverse effects

8. STUDY OUTLINE

8.1 Study design and rational of the chosen approaches

The total sample size will be 56 patients. Patients from cohort 1 (n=8-12), 4-6 female and 4-6 male (each cohort minimum 3) will be used in the final analysis. Patients with locally advanced or metastatic NETs of any site will be recruited from the Endocrinology, Surgical and Oncology Outpatients clinic, Hammersmith and Royal Free Hospitals. After obtaining informed consent, eligible patients will have blood taken at baseline for FBC, EUC, LFTs (routine clinical practice), and serum biomarkers. Patients will undergo routine staging. In addition, patients will undergo $[^{18}\text{F}]\text{-FET-}\beta\text{AG-TOCA}$ PET/CT scanning at Imanova. Patients' original diagnostic tumour biopsy (paraffin fixed) will be obtained.

8.1.1 Cohort 1. Dosimetry and safety study in patients with histological diagnosis of NETs of any site.

In this initial evaluation patients presenting for routine staging will be consented to undergo whole body dynamic scanning (multiple whole body scans up to 3.5 hours) with metabolite analysis in order to develop a suitable protocol for static scanning that will be used for patients in cohort 2. We will also calculate the internal radiation dosimetry, which may alter the administered dose in subsequent studies. Although we do not expect any toxicity, we will conduct detailed safety assessment in this group of patients. We require a minimum of 8 patients for final Dosimetry and safety analysis, which should include a minimum of either 3 male or 3 female subjects. To ensure both sexes are sufficiently represented in the final Dosimetry, for calculating effective dose, Cohort 1 will therefore include a minimum of 8, but up to 12 subjects.

8.1.2 Cohort 2. Open label study assessing tumoural uptake of $[^{18}\text{F}]\text{-FET-}\beta\text{AG-TOCA -PET}$ in patients with histological diagnosis of NETs of any site.

Patients presenting for routine staging will be consented to also undergo a static PET/CT imaging with $[^{18}\text{F}]\text{-FET-}\beta\text{AG-TOCA}$ in order to compare the clinical utility of $[^{18}\text{F}]\text{-FET-}\beta\text{AG-TOCA - PET/CT}$ with standard of care somatostatin receptor imaging. As a translational endpoint, patients will also be consented for retrieval of their pre-treatment biopsy specimen. Immunohistochemistry (IHC) will be performed for expression of SSTR1-5, which will be correlated with PET images from both tracers (see section 4.2 for Summary)

9. ELIGIBILITY

9.1 Inclusion criteria

1. Written informed consent
2. Age \geq 18 years
3. Histological diagnosis of NET of any site, except where ENETS criteria does not mandate histology for confirmation of diagnosis or patients who have a positive $^{68}\text{Gallium-peptide}$ scan in whom NET diagnosis is pre-operatively definitive.
4. Locally advanced or metastatic disease
5. Eastern Cooperative Oncology Group (ECOG) performance status of ≤ 2 (appendix A)
6. Life expectancy > 3 months
7. Measurable disease defined as a lesion that can be accurately measured in at least one dimension with the longest diameter $\geq 10\text{mm}$ using conventional techniques
8. Somatostatin receptor imaging within 6 months. (if patient does not have somatostatin receptor imaging they may also be included provided they have measurable disease ($\geq 10\text{mm}$) on conventional imaging).
9. Adequate organ system function as defined in Table 1

Table 1 clinical laboratory parameters

| System | Laboratory Values |
|-------------------------------------------------------------------|------------------------------------------------------------------------------------------|
| Hematologic | |
| Absolute neutrophil count (ANC) | $\geq 1.5 \times 10^9/\text{L}$ |
| Hemoglobin ¹ | $\geq 9 \text{ g/dL}$ (5.6 mmol/L) |
| Platelets | $\geq 100 \times 10^9/\text{L}$ |
| Prothrombin time (PT) or international normalized ratio (INR) | $\leq 1.2 \times$ upper limit of normal (ULN) |
| Partial thromboplastin time (PTT) | $\leq 1.2 \times$ ULN |
| Hepatic² | |
| Total bilirubin | $\leq 1.5 \times$ ULN |
| AST and ALT | $\leq 2.5 \times$ ULN |
| Renal | |
| Serum creatinine | $\leq 1.5 \text{ mg/dL}$ (133 $\mu\text{mol/L}$) |
| Or, if greater than 1.5 mg/dL: Calculated creatinine clearance | $\geq 50 \text{ mL/min}$ |
| 1 | Subjects may not have had a transfusion within 7 days of screening assessment. |
| 2 | Concomitant elevations in bilirubin and AST/ALT above $1.0 \times$ ULN are not permitted |

9.2 Exclusion Criteria

1. Patients received chemotherapy within 3 weeks of study

2. Patients received radiotherapy within 4 weeks of study
3. Active uncontrolled infections, gastrointestinal disease, haemolysis or any serious co-existing medical illness
4. Psychological, familial, sociological or geographical condition potentially hampering compliance with the study protocol and follow-up schedule
5. Pregnant or lactating women
6. Females of childbearing potential who are unwilling to avoid pregnancy, for the duration of the study
7. Presence of any underlying medical conditions which in the investigators opinion would make the patients unsuitable for treatment
8. Patient not expected to be able to tolerate the scanning sessions

10. COMPLETION OR EARLY WITHDRAWAL

10.1 Subject completion

A completed subject is one who has completed all phases of the study. The end of the study is defined as the last subject's last visit.

10.2 Withdrawal criteria

Whatever the disease status, the treatment will always be discontinued in case of patient refusal.

Each patient is free to withdraw from the study at any time.

A complete final evaluation at the time of the subject's withdrawal will be made and an explanation given of why the patient is withdrawing or being withdrawn from the study.

The reason for non-completion and the date and time of the last contact with the patient must be noted in the case report form (CRF).

In the case of patients withdrawal before or after dosing (ie, non-evaluable subjects) additional patients may be enrolled to reach a total of 56 evaluable patients.

10.3 Blinding

This is an open label study, therefore blinding is not applicable.

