7.2.2 Secondary

2. Compare diagnostic efficacy of [¹⁸F]-FET-βAG-TOCA in those patients who have had or not had or are due to have [⁶⁸Ga]-DOTA-peptide imaging. A power of $\geq 80\%$ has been chosen to conclude non-inferiority equivalence.

*Note** (All patients with a histological diagnosis of NET and lesion on CT is $\geq 1\text{cm}$ irrespective of whether they have had a [⁶⁸Ga]-DOTA-peptide scan or are waiting for one as part of their management will be included in study).*

3. Comparison of [¹⁸F]-FET-βAG-TOCA PET/CT scan and central review (nuclear medicine and radiology physician experts) of all imaging received by patient. (To account for any discrepancy that may exist between CT, [⁶⁸Ga]-DOTA-peptide imaging and [¹⁸F]-FET-βAG-TOCA PET/CT scan, then patients will be offered an MRI scan.

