11.1 Screening period (Day -30 to Day 0)

- Patients will be screened up to 30 days before tracer administration and confirm eligibility. At the screening visit demographic data/baseline characteristics, medical history, and medication will be recorded. All female subjects of childbearing potential will undergo a pregnancy test.
- Signed and dated informed consent must be obtained from all subjects prior to any protocol specific procedures being performed.
- Blood samples for serum biochemistry and haematology, will be drawn from venous blood if not already taken as part of subjects standard care within 30 days of tracer administration. ;.
- Vital signs and pulse oximetry, will be recorded and a physical examination including a limited neurological examination will be performed.
- If [⁶⁸Ga]-DOTA-peptide imaging PET/CT has been performed within 6 months of [¹⁸F]-FET-βAG- TOCA PET/CT, scans will be retrieved.

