11.4 PET parameters

Attenuation corrected images will be reconstructed. Regions of interest will be drawn around the tumour to derive semi-quantitative uptake parameters, SUV (standardized uptake value) and AUC (area under curve, total activity over scanning time). Venous blood samples will be taken for assessment of counts during the [¹⁸F]-FET- β AG-TOCA scan in cohort 1. These bloods will be used to generate the blood input function that is required to derive uptake tracer

parameters such as Ki (rate constant for net irreversible uptake) and FRT (fractional retention of tracer) which will be used to set scanning parameters for cohort 2.

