13.2 Radiation dose

The total effective dose (ED) received from the PET-CT scan is estimated to be 12mSv for cohort 1 and 14 mSv for cohort 2. In a dosimetry study such as this, the estimate is necessarily uncertain but a conservative approach has been taken that will overestimate the effective dose by using a high dose conversion factor of 0.04 mSv/MBq injected activity. The total effective dose of 14 mSv (cohort2) is equivalent to about 6 times the average yearly exposure (2.3 mSv) from natural background radiation in the United Kingdom. For an adult in good health, this exposure would result in a risk of around 1 in 1600 (cohort1) and 1 in 1400 (cohort2) of contracting a fatal cancer. However, for someone in the planned study groups who have shorter life expectancy than the general population it represents a significantly lower risk. Note that as part of the standard practice for patients included in this study, a single [⁶⁸Ga] Dotatate PET/CT scan will be performed; this is one of the entry qualifications but is not an additional examination that is part of the research protocol.

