14.2.1 Power and sample size determination

Power for the Wilcoxon signed-rank test is calculated by simulation using a truncated log-normal distribution parameterized according to Kabasakal et al.¹⁵ (median = 5, range = 1 to 25) to sample the total number of lesions in patients

across a range of samples. With a total of $N = 48$ patients assessed by both modalities, there will be 80% power to conclude non-inferiority equivalence if the two methods are equivalent ($\Delta = 0$).

The distributions of number of lesions detected by $[^{18}\text{F}]\text{-FET-}\beta\text{AG-TOCA}$ – PET/CT and by $[^{68}\text{Ga}]\text{-DOTA-peptide-PET/CT}$ will be summarized, and will be compared using the Wilcoxon signed-rank test with the pre-specified level of equivalence of $\Delta = 0.64$ and a one-sided alpha= 0.1.

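### Section 10.3 treats open-label administration as ruling out blinding, and the available text has no rule that the two PET scans compared on lesion counts are read separately or masked to each other

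*Combined protocol and SAP*

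**What the plan says.** Section 10.3 consists of one sentence: "This is an open label study, therefore blinding is not applicable". It does not distinguish between giving the tracer and reading the images.

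Section 14.2.1 describes the comparison that depends on reading. The numbers of lesions found by 18F-FET-βAG-TOCA PET/CT and by 68Ga-DOTA-peptide PET/CT "will be compared using the Wilcoxon signed-rank test with the pre-specified level of equivalence" of 0.64, at one-sided alpha 0.1. The sample size follows from it: with 48 "patients assessed by both modalities, there will be 80% power to conclude non-inferiority equivalence" if the methods do not differ. Section 14.2 adds per-patient and per-lesion McNemar comparisons with standard somatostatin receptor imaging.

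Section 11.4 deals with image analysis: "Regions of interest will be drawn around the tumour to derive semi-quantitative uptake parameters". It goes on to kinetic parameters. It does not say who counts lesions or what that reader may see.

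Three places bear on whether the 68Ga result is known when the 18F scan is read:

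- Section 9.1, item 3, lets a positive 68Ga scan stand in for histology in patients with such a "scan in whom NET diagnosis is pre-operatively definitive".
- Section 11.1 says that, where a 68Ga scan was done within 6 months of the study scan, "scans will be retrieved".
- Section 13.2 says of the 68Ga scan that "this is one of the entry qualifications but is not an additional examination that is part of the research protocol".

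Section 7.2.2, item 2, includes 18F imaging "in those patients who have had or not had or are due to have" the 68Ga scan, so the order of the two scans varies. Item 3 plans an expert central review of all the patient's imaging, with an MRI offered where findings disagree.

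**The concern.** Section 10.3 draws a conclusion that does not follow. A study can be open label for the product and still have its images read by someone who does not know the other result. Masking matters here because a lesion count is a reader's judgement, and the planned test uses the difference between two such counts in the same patient.

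The direction of the bias depends on which scan is known first.

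- **68Ga known first.** The reader may mark on the 18F scan lesions that would not have been called from that scan alone. If the new tracer truly finds fewer lesions, the deficit shrinks. In a superiority test that would be conservative; in a non-inferiority test it favours the conclusion sought.
- **18F known first.** Lesions seen on the 18F scan may be added to the 68Ga count. A true deficit then looks larger, or one appears where none exists, and the new tracer is penalised.

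Either way, the result of 14.2.1 would partly reflect the order and conditions of reading instead of the tracers.

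**Working it through.** **Text check.** Section 10.3 declares blinding not applicable. Section 11.4 covers uptake and kinetic parameters only. The central review in 7.2.2, item 3, is neither masked nor separate as written. Sections 14.2 and 14.2.1 give tests but no reading rule. Section 8.1.2 refers to the summary in 4.2, of which only the heading and a footnote are available. No available passage sets separate reads, masking or reading order.

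**Inputs from section 14.2.1.** N = 48, margin 0.64, one-sided alpha 0.1, power 80% at a true difference of 0. The section gives neither the SD of the paired difference nor a unit for 0.64.

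**The plan's 80%.** It cannot be confirmed or refuted without that SD. Simulations of the signed-rank test using the plan's median of 5 and range of 1 to 25, with assumed log-SDs, gave about 26–44% power if the two counts are independent. They gave about 95–100% if both tracers sample a shared lesion total. The stated 80% lies between. I therefore solve for the SD that gives 80% under a normal model, taking 0.64 as lesions per patient:

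- SD = 0.64 × √48 / (1.2816 + 0.8416) = 4.434 / 2.1232 = 2.09
- SE = 2.088 / √48 = 0.301
- Power at no difference = Φ(0.64/0.301 − 1.2816) = 0.80, by construction

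**Illustration.** Assume reading bias shifts the mean paired difference by 0.2 lesions, net over all 48 patients.

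- Towards the new tracer, true deficit 0.64: Φ(0.2/0.301 − 1.2816) = Φ(−0.62) = 0.27, against a nominal 0.10. Simulating the signed-rank test with normal differences gave 0.26.
- Against the new tracer, no true difference: Φ((0.64 − 0.2)/0.301 − 1.2816) = Φ(0.18) = 0.57, against 0.80.

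**Sensitivity to the assumed values.**

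- A shift of half that size, 0.1: error Φ(0.1/0.301 − 1.2816) = Φ(−0.95) = 0.17; power Φ(0.54/0.301 − 1.2816) = Φ(0.51) = 0.70.
- A shift of 0.2 with SD 1.5 or 3: error 0.36 or 0.21. These SDs correspond to 95% or 58% power without bias, so they do not match the plan's 80%.

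**The case against.** The strongest reply concerns weight. This is a Phase 1 study. Cohort 1's primary endpoints are biodistribution and dosimetry, and cohort 2's is tumoural uptake; lesion-count non-inferiority is secondary. Section 10.3 can be read as an ordinary remark about tracer administration, and it does not forbid masked reading. A rule might also stand in the 4.2 chart or in an imaging document outside this file. All of this stands and limits the point. It does not remove it: the lesion-count test is the only stated basis for N = 48, and anyone following 10.3 as worded would see no reason to mask the reads.

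Three stronger readings are tempting, and the documents do not support them.

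- *Unmasked reading always pulls the two counts together and so always helps the new tracer.* This fails for patients imaged with 18F first. In a simulated count model, carrying 10% of 18F-only lesions over to the 68Ga read widened a mean deficit of 0.64 to about 0.68–0.74. The plan does not say how many patients fall in each order, so the net direction is unknown.
- *The 68Ga result is known for every patient.* Section 13.2 suggests this, but section 9.1, item 8, admits patients without somatostatin receptor imaging. The two passages conflict, so 13.2 is weak evidence by itself.
- *The error rate becomes far higher than 27%.* In the count model, with assumed detection rates, non-inferiority was declared in 57–67% of runs when 10% of 68Ga-only lesions were carried over. The same model gives 29–44% with no reading bias, and about 99–100% power at zero difference. It is therefore not the plan's 80% scenario, and the excess cannot be put down to 10.3. In that model 10% reverse carry-over left power at 98% or more, so the fall from 80% to 57% is also specific to the normal illustration.

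**Conclusion.** The concern holds in a limited form. Section 10.3 wrongly infers from open-label administration that blinding does not apply, and the available text leaves the within-patient lesion counts of 14.2.1 open to reading with the other scan known. The bias can run either way: towards non-inferiority where an earlier 68Ga scan is known, against the new tracer where the 18F scan is known first.

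The size is not determined by the documents. The figures of 27% error and 57% power rest on four assumptions: 0.64 means lesions per patient, differences are normal, the SD is the one implied by 80% power, and the net shift is 0.2 lesions. They show that a shift well inside the margin would matter; they do not estimate what would happen. The primary endpoints are not called into question by this point. The change should be made, because the comparison that sized the study depends on these reads and a reader's knowledge cannot be undone afterwards.

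**What to change.** Reword 10.3 so that open label refers to tracer administration only. Then add a reading rule, for patients who have both scans:

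- The 18F and 68Ga PET scans are read for lesion counts by the experts already planned for central review.
- Reads take place in separate sessions with a stated interval, in random order, each masked to the other PET scan and its report.
- The counts are locked before the central review of all imaging and before any MRI offered for a discrepancy.
- The locked counts are used in 14.2.1 and in the per-patient and per-lesion comparisons with 68Ga PET in 14.2.

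This is a cheap improvement: wording and a reading schedule, with no new scans or patients and no change to N or alpha. That no new readers are needed is an assumption, since the plan does not say who counts lesions. The downside is time. Reads take longer to schedule, and for patients awaiting 68Ga imaging the paired read must wait until that standard-of-care scan is available. A step to retrieve it must be added, because 11.1 covers only scans already done.

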11. STUDY PROCEDURES

Each patient will have one session of PET/CT scanning. Patients in cohort 1 will be required to have an overnight stay following their scan whilst those in cohort 2 will have up to a 70 minute scan and will be discharged home following the scan. All efficacy and safety measurements obtained during the

course of the study are summarised in the Study Schedule of Events in table 1 and 2.

Table 2. Study Schedule of Events for cohort 1.

| | -30 days screening | -30 to -5 min | -2 min | Dose | +2 min | +5 min | +10 min | +15 min | +30 min | +1 hour | +1 hour 30 min | +2 h 30 min | +4 hours | + 24 hours |
|-------------------------------------------------------------------|--------------------|---------------|--------|------|--------|--------|---------|---------|---------|---------|----------------|-------------|----------|------------|
| Informed Consent | • | | | | | | | | | | | | | |
| Entry Criteria | • | | | | | | | | | | | | | |
| Demographic Information | • | | | | | | | | | | | | | |
| Medical History | • | | | | | | | | | | | | | |
| Prior/Concomitant Medication | • | • | | | | | | | | | | | | |
| Physical Exam | • | • | | | | | | | | | | | | • |
| Injection Site Monitoring | | | • | | • | | • | | | | • | | • | • |
| Pregnancy Test | • | • | | | | | | | | | | | | |
| ECG ¹ | • | • | • | • | • | • | • | • | • | • | • | • | • | • |
| Pulse Oximetry ² | • | • | • | • | • | • | • | • | • | • | • | • | • | • |
| Vital Signs | • | • | • | | • | • | • | • | • | • | • | • | • | • |
| Blood (Serum Biochemistry, Haematology, Coagulation) ³ | • | • | | | | | | | • | | • | • | • | • |
| Urinalysis ⁴ | • | • | | | | | | | • | • | • | • | • | • |
| Pre-administration Events | | | | | | | | | | | | | | |
| Transmission Scan | | • | | | | | | | | | | | | |
| [¹⁸ F]-FET-βAG-TOCA injection | | | | • | | | | | | | | | | |
| Post-administration Events ⁵ | | | | | | | | | | | | | | |
| PET Imaging ⁶ | | | | | | | | | | | | | | |
| Blood and Plasma for Activity Counting | | | | | | • | • | • | • | • | • | • | | |
| Urine ⁴ for Activity Counting | | | | | | | | | | | | | | |

min=minutes

¹ Continuous ECG performed from -5 min to +15 min. Lead II may be used for continuous monitoring. 12-lead ECG should be recorded at the times indicated ECG should remain under continuous supervision and additional print outs obtained if any abnormality is detected

² At baseline, before vital signs and pulse oximetry are measured, the subject should be resting for at least 5 minutes (if possible)

³ All blood samples for patients will be taken from venous blood.

⁴ Time points indicated are preferred time points, urine will be collected as voided

⁵ Events will be collected throughout the subjects participation in the study

⁶ PET Imaging will be taken at 4 discrete time points for up to 4 hours post administration, with resting periods in between

* Shaded areas depict continuous monitoring

Table 3. Study Schedule of Events for cohort 2.

| | ≤ 30 days | -180 to -5 min | Dose | ≥ 70 - min | END OF SCAN |
|--------------------------------------------------------|----------------|----------------|------|-----------------|-------------|
| Informed Consent | • | | | | |
| Entry Criteria | • | | | | |
| Demographic Information | • | | | | |
| Medical History | • | | | | |
| Prior/Concomitant Medication | • | | | | |
| Physical Exam | • | | | | |
| Pregnancy Test ^{4,5} | • | • | | | |
| Pulse Oximetry ^{1,5} | • | • | | | |
| Vital Signs ^{1,5} | • | • | | | |
| Blood (Serum Biochemistry, Haematology) ² | • | | | | |
| [¹⁸ F]-FET-βAG-TOCA injection (max 370MBq) | | | • | | |
| PET/CT Imaging | | | | | |
| Adverse event monitoring ³ | | | | | |

min=minutes

¹ At baseline, before vital signs and pulse oximetry are measured, the subject should be resting for at least 5 minutes (if possible)

² All blood samples for patients will be taken from venous blood. If blood results are available which have been taken as part of subjects standard care (within 30 days of study scan), these do not need to be repeated.

³ Events will be collected throughout the subjects participation in the study

⁴ Women of childbearing potential.

⁵ Where screening and PET scan are on same day, procedure is done once

*Shaded areas depict continuous monitoring

